To assess the robustness of the primary MMRM results to the possible violation of the missing-at-random assumption, a sensitivity analysis using a pattern-mixture model based on non-future dependent missing value restrictions (Kenward et al, 2003) will be performed. The pattern for the pattern-mixture model will be defined by the patient's last visit with observed value. The observed MADRS total score at a visit is assumed to have a linear relationship with the patient's prior measurements. The missing values will be imputed under the assumption that the distribution of the missing observations differs from the observed only by a shift parameter value Δ . The dataset with missing values will be analyzed using the same model as the primary analysis for between-treatment group comparisons at the end of the treatment. The imputation of missing values and the analysis will be performed multiple times and the inference of this sensitivity analysis will be based on the combined estimates using the standard multiple imputation technique. The values of Δ will be selected as 0 to 8.

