9.1 PRIMARY EFFICACY PARAMETER

The primary efficacy parameter will be the change from baseline to Day 21 in MADRS total score for the mITT population. The MADRS total score is the sum of the 10 individual items. If more than 2 items are missing, then the total score will be set to missing. If there are multiple assessments of MADRS total score for the same nominal visit of a patient, only the last assessment will be used in the analysis.

The primary efficacy parameter will be analyzed using a mixed model for repeated measures (MMRM) with treatment group, pooled study center, visit, placebo responder status at Day 7, and treatment group-by-visit interaction as the fixed effects, and Day 0 MADRS total score, baseline MADRS total score, Day 0 MADRS total score-by-visit and baseline MADRS total score-by-visit interactions as covariates. An unstructured covariance matrix is used to model the covariance of change in scores within patients. The Kenward-Roger approximation will be used to estimate denominator degrees of freedom ([Kenward et al, 1997](#)). The analysis will be performed based on all post-randomization data using only the observed cases without imputation of missing values.

In the case that the MMRM model with unstructured covariance fails to converge with the default algorithm, then the Fisher scoring algorithm will be used to provide better initial values of the covariance parameters; if the model still does not converge, a simplified model without term for study center will be used to find the initial values of the covariance parameters. In the rare event that the model still does not converge after using those initial values, simplified covariance structures will be used to fit the model in the following order until the model converges: (1) ante-dependence, (2) heterogeneous autoregressive, (3) Toeplitz, and (4) compound symmetry.

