To assess the robustness of the primary MMRM results to the possible violation of the missing-at-random assumption, a sensitivity analysis using a pattern-mixture model based on non-future dependent missing value restrictions (Kenward et al, 2003) will be performed. The pattern for the pattern-mixture model will be defined by the patient's last visit with observed value. The observed MADRS total score at a visit is assumed to have a linear relationship with the patient's prior measurements. The missing values will be imputed under the assumption that the distribution of the missing observations differs from the observed only by a shift parameter value Δ . The dataset with missing values will be analyzed using the same model as the primary analysis for between-treatment group comparisons. The imputation of missing values and the analysis will be performed multiple times and the inference of this sensitivity analysis will be based on the combined estimates using the standard multiple imputation technique. The values for Δ will be selected as 0 to 8.

[figure not shown]

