Note that the two distributions only differ from a shift (Δ) parameter. When $\Delta = 0$, the missing value y_s in Pattern $s-1$ is imputed based on the distribution of all observed data up to Visit s , as a result, leading to missing at random (MAR) missingness. When $\Delta \neq 0$, (8) will introduce a scenario of MNAR. A similar idea was also presented in the recent publication “*The Prevention and Treatment of Missing Data in Clinical Trials*” by the National Academy Press. The selection of the plausible values for the shift parameter (Δ) is discussed in Section 3.

Note that per recommendation in Wang and Daniels (2011), only the observed data within the pattern is assumed to be multivariate normal. The observed data distribution can be expressed in terms of the marginal distribution of baseline measurements and the conditional distributions of postbaseline measurements given earlier measurements. Assuming that these distributions are normal, the linear regression of each observation on prior observations will yield least-squares estimates of model parameters that can be utilized for independent posterior draws of model parameters for observed data. The multiple imputation approach will be used to estimate the overall mean at the final time point.

2. Imputation Procedure

All the missing data will be imputed to create a complete dataset, then statistical analysis can be performed using appropriate techniques such as **MMRM**. The imputation **can accommodate MNAR missing data mechanisms**, based on the theory discussed in the above sections.

The model parameters for each dropout pattern, i.e., the mean, variance and proportions of observations in each pattern, are drawn from their posterior distributions prior to the imputation of missing data for a single imputation.

The details of imputation within a pattern, say Pattern t , are as the following:

Step 1. Impute the first missing value y_{t+1} for each patient in Pattern t ($t = 1, \dots, T-1$):

- a. Compute estimates of mixture probabilities $\lambda_{s-1,j}$ in (7) with $s = t+1$ given the posterior draw of proportions of observations in each pattern and the posterior draw of regression parameters for the observed data.

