- b. Draw a random integer from $\{s, \dots, T\}$ to index a component distribution on the right hand side of (6), using mixture probabilities obtained in a). Draw y_{t+1}^* from the identified component normal distribution. Impute the missing y_{t+1} as $\tilde{y}_{t+1} = y_{t+1}^* + \Delta$.

Step 2. Impute the rest of the missing values of $y_{t+2}, y_{t+3}, \dots, y_T$ for patients in Pattern t:

Starting with imputation for y_{t+2} , first, similar to Step 1, draw y_{t+2}^* from the normal mixture (6) based on the observed y_1, \dots, y_t and the already imputed \tilde{y}_{t+1} for the patient. Then the missing y_{t+2} is imputed as $\tilde{y}_{t+2} = y_{t+2}^* + \Delta$ with probability δ_{t+1} and as $\tilde{y}_{t+2} = y_{t+2}^*$ with probability $1 - \delta_{t+1}$, where the mixture probability $\delta_{t+1} = \omega_{t+1,t+1}$ is obtained from (4) given the posterior draw of proportions of observations in each pattern and the posterior draw of regression parameters for the observed data.

Missing values of y_{t+3} through y_T can be imputed similarly as y_{t+2} .

To summarize, the imputations of y_{t+1} through y_T is done recursively within each Pattern t (for all $t = 1, \dots, T - 1$) to create a complete dataset after imputation is done for all patterns with missing values.

The above imputation procedure is applied to all subjects in each missing data pattern to create a single imputed data set. Repeating the process of drawing parameters from the posterior distribution and imputing missing data given the posterior draw m times will yield m imputed data sets. The observed or imputed values at the final data point are averaged to obtain the overall mean estimate for each imputed data set, and the multiple imputation estimate is obtained by averaging the estimates across m imputations.

In this sensitivity analysis, m is set to equal to 20. The value of m is discussed in the context of imputation efficiency in standard multiple imputation theory (Rubin, 1987, p. 114), and $m = 20$ would provide at least 96% of relative efficiency as compared with using an large number of imputations (SAS/STAT User's Guide, p. 3796).

3. Determination of the Shift Parameter Values

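### SAP Appendix II contains an averaging step that contradicts the MMRM analysis of the imputed data required by SAP 9.1; if followed, the shift-0 run would not reproduce the primary estimate

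*SAP*

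**What the plan says.** **SAP 9.1** plans a pattern-mixture sensitivity analysis of the primary endpoint with shifts from 0 to 8. On the analysis step it says: "The dataset with missing values will be analyzed using the same model as the primary analysis for between-treatment group comparisons". It adds that "the inference of this sensitivity analysis will be based on the combined estimates using the standard multiple imputation technique". The primary model has treatment, pooled center, visit, Day 7 responder status and treatment-by-visit as fixed effects, with "Day 0 MADRS total score, baseline MADRS total score, Day 0 MADRS total score-by-visit and baseline MADRS total score-by-visit interactions as covariates".

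**Protocol 9.7.5.1** agrees: the data "will be analyzed using the same model as the primary analysis for between-treatment group comparisons at the end of the treatment".

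**SAP Appendix II** makes three statements that bear on the same step:
- The end of part 1 gives the target: "The multiple imputation approach will be used to estimate the overall mean at the final time point".
- The start of part 2 says the missing data are imputed to form a complete dataset, and "then statistical analysis can be performed using appropriate techniques such as" MMRM.
- The end of part 2, just before m is set to 20, says: "The observed or imputed values at the final data point are averaged to obtain the overall mean estimate for each imputed data set". The multiple-imputation estimate is then the average of those means over the m imputations.

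Appendix II, part 1, also states that a shift of 0 corresponds to missing at random. Nothing in the visible text says which statement governs, or whether imputation is done by treatment arm.

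**The concern.** A missing-data sensitivity analysis should differ from the primary analysis only in what it assumes about the missing values. The shift-0 run is its anchor: it keeps the primary assumption, so it should return the primary estimate up to imputation noise. The larger shifts are then read against that anchor.

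The averaging step breaks this link. As written it produces a mean for each dataset. To give a treatment effect, it would have to be applied in each arm and the two means subtracted. That difference carries no adjustment for center, responder status, Day 0 score or baseline score. A chance imbalance in the pre-randomization scores would enter the estimate directly. A reader could then take the difference from the primary result as sensitivity to missing data when it comes from a change of estimator. The SAP reports overall drop-out below 5%, so at small shifts the estimator effect could outweigh the missing-data effect under test.

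The step also combines point estimates only. It gives no within- or between-imputation variance, although SAP 9.1 bases inference on standard multiple-imputation combination.

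**Working it through.** **Inputs.** From SAP 13.0: 230 per arm, SD 8.7 (7.4 in this study's blinded review), correlation 0.5 between repeated measures, a 3.25-point difference, two-sided 0.05. Assumptions: 8.7 is the SD of the change; the correlation is the same between all visits; the correlation range is 0.3 to 0.7; and 3.25, which the current text gives for the original calculation, still applies.

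**The plan's own figure.** n per arm = 2(1.960 + 1.282)² × 8.7² / 3.25² = 151. Dividing by 0.85 for drop-out gives 178 per arm, or 356 in total, against the plan's 360. The inputs are therefore a fair basis.

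**Standard errors with complete data.** Let ρ be the correlation and s = 8.7/√(2(1−ρ)) the SD of a single score. At ρ = 0.5, s = 8.7.
- Unadjusted change: 8.7 × √(2/230) = 0.811. The unadjusted Day 21 score gives the same value at ρ = 0.5.
- Adjusted for baseline only: 0.811 × √(1 − 0.5²) = 0.703.
- Adjusted for Day 0 and baseline: R² = 2ρ²/(1+ρ) = 0.333, so 0.811 × √0.667 = 0.662.
- Inflation: 0.811/0.703 = 1.15 and 0.811/0.662 = 1.22.

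**Range over ρ** (change scores, both covariates):

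| ρ | Unadjusted SE | Adjusted SE | Ratio |
|---|---|---|---|
| 0.3 | 0.811 | 0.636 | 1.28 |
| 0.5 | 0.811 | 0.662 | 1.22 |
| 0.7 | 0.811 | 0.682 | 1.19 |

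**Gap between the two estimates in one trial.** The gap has mean zero. With baseline only, its SD is 0.5 × 0.811 = 0.41. With both covariates it is √(0.811² − 0.662²) = 0.47. At SD 7.4 with baseline only it is 0.35.

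**Significance at 3.25 points** (both covariates). Power is Φ(3.25/0.662 − 1.96) = 99.8% adjusted and Φ(3.25/0.811 − 1.96) = 98.0% unadjusted. Treating the unadjusted estimate as the adjusted one plus an independent gap of SD 0.47, 1.9% of significant adjusted results become non-significant. At SD 7.4 the figure is 0.3%.

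**Simulation with drop-out.** 600 trials per setting, six post-baseline visits, SD 8.7, ρ = 0.5, missing at random, shift 0, m = 20, imputation by arm. Center, responder status and Day 0 score were omitted because the documents give no values for them.

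| Setting | SD of gap, averaging | SD of gap, adjusted model | Gap over 0.5, averaging | Gap over 0.5, adjusted model |
|---|---|---|---|---|
| 230 per arm, 5% drop-out | 0.41 | 0.04 | 22% | 0% |
| 180 per arm, 15% drop-out | 0.48 | 0.10 | 30% | 0% |

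In the first setting the mean estimates were −3.29 (primary), −3.31 (averaging) and −3.29 (adjusted model on imputed data).

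**Imputation not by arm.** When the imputation pooled the arms and left treatment out, the adjusted shift-0 estimate moved toward zero: from −3.23 to −3.17 at 5% drop-out, and from −3.27 to −3.08 at 15%. Restoring the MMRM alone would then not fully anchor the shift-0 run.

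**The case against.** The strongest reply is that the estimator is already fixed. The main text of both documents says the sensitivity data "will be analyzed using the same model as the primary analysis for between-treatment group comparisons", and SAP 9.1 names the combination rule. The appendix explains the imputation, nothing gives it precedence, and it names MMRM itself. The averaging sentence mentions no arm, contrast or test, so it may be only a generic description of multiple imputation. The SAP's history of changes also records that the SAS code was moved to a separate document, which may implement the MMRM.

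Most of this stands. A reader might infer that the SAP has replaced the MMRM with an unadjusted average. The documents do not support that: they contain a contradiction, and the better-placed statement favors the MMRM. The missing variance is likewise supplied by SAP 9.1 if that section governs.

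The sentence itself remains a problem. It is declarative and is the last estimation step in the procedure, whereas the appendix's reference to MMRM is permissive. The appendix states the same target twice, and that target is a mean and not a treatment difference. A code document outside the SAP does not settle what the SAP prespecifies.

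**Conclusion.** Wrong as written, with low severity. The averaging sentence conflicts with SAP 9.1 and Protocol 9.7.5.1 and would give a poorer sensitivity analysis if followed. On the plan's figures, averaging by arm raises the standard error from 0.66–0.70 to 0.81 and puts a random gap with an SD of about 0.4 points between the shift-0 and primary estimates. For change scores with both covariates the inflation is about 19% to 28% over correlations 0.3 to 0.7. All of this is conditional on the averaging sentence being used, and rests on equal correlations and the assumed SD of change.

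Two stronger readings should be resisted:
- **Bias.** The expected gap under missing at random is zero. The loss is in precision and comparability.
- **Frequent loss of significance.** At 3.25 points it is about 2%. Figures near 21% need a true effect of 2.0 points, which appears nowhere in the documents. Inflation as high as 54% needs correlation 0.7 and averaging of Day 21 scores, while the primary parameter is a change from baseline.

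The primary test and its type I error are unaffected.

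**What to change.** 1. In Appendix II, part 2, replace the averaging sentence with: *Each of the m completed datasets will be analyzed with the primary MMRM of Section 9.1; the LS mean treatment difference at Day 21 and its standard error will be combined across the m datasets by Rubin's rules.*
2. At the end of Appendix II, part 1, name the Day 21 treatment difference as the quantity estimated, in place of the overall mean.
3. In SAP 9.1, say that the model is fitted to each imputed dataset; the sentence now refers to the dataset that still has missing values.
4. State that imputation is done separately by treatment arm, or that the imputation model includes treatment, so that shift 0 reproduces the primary analysis up to imputation noise.

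The cost is a few sentences of SAP text. SAP 9.1 already calls for repeated imputation and MMRM fitting. No new data are needed and patients are not affected.
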